5.0 Study Procedures

5.1 Study Design

Research Design: A multi-center, repeat-measures randomized controlled mixed-methods trial.

Study Population: The proposed study will focus on Internal Medicine physicians who are part of inpatient care teams and nurses providing care on medical and medical/surgical units at LTC Charles S. Kettles VAMC in Ann Arbor, MI and MEDVAMC in Houston, TX. Medical students, surgical physicians, and physicians on sub-specialty teams will not be included. At both participating facilities the inpatient care teams are predominately composed of 1 attending, 1 senior resident, 2 interns, and up to 3 medical or physician assistant students. Interns and senior residents are usually assigned to a team for 4-week blocks (occasionally 2 weeks), while attendings rotate approximately every 2 weeks. The Ann Arbor VAMC has 3 medical or medical/surgical inpatient units, while MEDVAMC has 5 units. At both facilities each nursing unit employs between 20-30 nurses. We will aim to recruit approximately 30 attendings, 72 residents and 40 nurses at Ann Arbor VAMC. As MEDVAMC is larger, with a greater number of inpatient care teams and nursing units than the Ann Arbor VAMC, we will aim to recruit approximately 40 attendings, 72 residents and 90 nurses. Our target study sample size is a total of 344 physicians and nurses (167 intervention/177 control). For Aim 3, we plan to interview approximately 8 physician team members and 4-6 nurses from the intervention arm at each site.

General Study Overview and Outcome Measures:

A summary of the proposed study activities at each participating site is presented in **Table 2** below.

Table 2: Overview of Study Activities at Each Study Site

| Study Detail | Physicians | Nurses |
|----------------------------------|--|--|
| Target | Attendings, senior residents and interns on inpatient medicine teams | Nurses on medical or medical/surgical units |
| Teams/Units Participating | 2 teams each month for 12 months randomized to intervention or control arm at each site | 2 units (1 intervention; 1 control) at Ann Arbor VAMC & 4 units (2 intervention; 2 control) at MEDVAMC randomized once & followed for 12-months |
| Estimated number of participants | 107 intervention and 107 control | 20 intervention and 20 control at Ann Arbor VAMC; 40 intervention and 50 control at MEDVAMC |
| Habituation Period | 1 month | 1 month |

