Randomization – At each study site the participating physician teams and nursing units will be randomly assigned into one of two study arms (intervention/control). For physician teams, this will occur on a rolling basis for 12 months with 2 physician teams randomly selected at each site each month for participation (1 intervention, 1 control). Once randomized, an email will be sent to the initial attending of the team introducing the study and asking them to reply to the email if they would prefer to opt out and not have their team participate in the randomized controlled trial. If the attending physician from a team refuses to allow their team to participate, the next team identified from the randomized list will be approached to participate. If a new attending joins the team mid-month, they will be approached to participate in the study, but will be automatically assigned to the same randomization group as the rest of their team.

Similarly, a total of 2 medical/surgical units from VAAHS (1 intervention, 1 control) and 4 medical/surgical units from MEDVAMC (2 intervention, 2 control) will be randomly selected to participate in the nurse portion of the project. The nurse manager for each

selected unit will then be approached to obtain approval for the unit to participate. If a nurse manager declines, the next unit on the list will be selected.

For both physicians and nurses, an independent statistician will allocate the teams and units in a concealed fashion, using a computer-generated randomization schema. The physicians and nurses from the intervention groups will receive both independent and group-facilitated mindfulness education, will be encouraged to use a mindfulness mobile app as a practice reminder and additional resource, and instructed to integrate moments of mindfulness with repeated episodes of hand hygiene during the course of caring for patients. The control groups will receive no such education or intervention and will continue as usual.

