that service rotation on weekdays (3-4 weeks). For the physician teams, which rotate each month, this process will be repeated monthly for 1 year with up to 24 patient-care teams from each participating site. Nurses from both the intervention and control medical/surgical units will be observed for hand hygiene for one month. Observers will be blinded to randomization of the physician teams and thus intervention status. Since nurses remain assigned to one unit for a much longer period of time, nursing units will only participate once during the study. This will result in two nursing units from VAAHHS and four nursing units from MEDVAMC participating. At the completion of the observations, the physicians and nurses will again be asked to complete FFMQ, WBI, and select PSHW questions. To assess sustainability of well-being, mindfulness, and hand hygiene perceptions, we will ask participants to repeat FFMQ, WBI, and select PSHW questions at 6-month post-intervention follow-up points. To assess sustainability of hand hygiene among physicians, select hand hygiene observations at 3 to 12 months post-intervention (based on team schedules) will be conducted. To assess hand hygiene sustainability among nurses, unit-based hand hygiene practices will be reassessed at 1-year post-intervention. To examine changes across survey time points, crosswalk files will be utilized. Participant names will not be on the survey. A study team member will assign the survey respondents an identification number to link repeat surveys.

As part of the intervention we will also collect measures of fidelity. This will include information from the Mindfulness Coach/Mindfulness for Clinicians mobile application including usage and responses from any assessments included in the app about the participant's level of mindfulness. We will also collect data on completion of the Ohio State University STREAM Mind Body modules. This data will be completely de-identified. Both programs do not collect any personal identifiers. Instead, participants will be asked to register with a study assigned code. The de-identified user data for each code will be shared back with the study team to assess fidelity.

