Covert observations within randomly selected areas within units will also be conducted for observing hand hygiene among nurse participants. Observations will be conducted for 1 month before the intervention and 1-month after the intervention. On all participating units, observations of nurse hand hygiene while entering and exiting patient rooms will be conducted. Hand hygiene duration among all nurses will also be captured upon room exit. Nurses will be observed for approximately 4 hours per day during the first part of their shift, as all nurses typically check in with each patient at the start of their shift. From covert locations within the unit, the observers will only be able to observe approximately 10 rooms at a time. They will move their location in the unit each day to ensure representation from different nurses. The number of times a nurse enters each patient room will vary, but we estimate at minimum each nurse will enter each room once per hour. Therefore, observing 10 patient rooms for 4 hours per day, with 2 observation points per entry would lead to approximately 80 hand hygiene moments observed per day per unit. Observing 3 units per arm for approximately 44 days total would lead to an estimated 7,040 nurse hand hygiene observations per study arm in total. As hand hygiene duration will also be recorded upon room exit, and estimated total of 3520 hand hygiene duration observations per study arm will be observed. In addition to the 1-month post-intervention observation period, we will also observe and collect 1 month of data on hand hygiene moments at 1-year post-intervention in the intervention and control units at both sites.

Collected data will be transferred from the paper observation data tool into a study database. The data analyst and project manager will be able to link these covert observations accordingly to intervention or control groups based on team and unit name.

Study surveys will be distributed in person using a paper survey and a postage-paid business reply envelope where feasible. Electronic surveys containing questions from FFMQ, WBI, and PSHW surveys will be generated. Study participants will be directed to a link to the survey tool (for the pre- and post-intervention, as well as 6-month post-intervention follow-up periods) and responses will be saved to a database managed by the study team.

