5.4 Inclusion/Exclusion Criteria

Aims 1 and 2:

For the nurse portion of the trial, 1 inpatient hospital unit at Ann Arbor VAMC and 2 units at MEDVAMC will be randomized to receive the intervention and an equal number of units at each site will be randomized to receive the control. All nurses on the selected units will be asked to participate in the voluntary study. Inclusion criteria are all nurses on the identified units. There are no exclusion criteria.

For the physician portion of the trial, we will focus on inpatient physician teaching teams, which typically include 1 attending physician, 1 senior resident, and 2-3 intern physicians (Year 1 residents). Inclusion criteria are physicians on inpatient medical teams. Exclusion criteria are medical students, surgical attendings, and physicians on sub-specialty teams. Attending physicians may be on service multiple times per year. Attending physicians will be allowed to participate in multiple months, however, once a physician has been randomized to the intervention arm, they will no longer be eligible to participate in the control arm of the study.

Aim 3:

In this aim we will conduct a qualitative evaluation to better understand the perception of the intervention and assess any barriers or facilitators encountered. The primary subjects will be nurses and physicians that participated in the intervention. Inclusion criteria for this aim is being a nurse or physician that participated in the intervention. There are no exclusion criteria.

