5.6 Data Analysis

Quantitative Statistical Analysis (Aims 1 and 2): Differences in hand hygiene adherence and duration between intervention and control groups will be assessed using Fisher's exact test and t-test, as appropriate. Risk differences in adherence to duration of hand hygiene will be calculated for both intervention and control groups. Because the primary outcomes for Aim 1 (i.e., hand hygiene adherence and duration) are expected to occur frequently, we will use generalized linear models to evaluate differences in hand hygiene adherence and duration for the intervention versus control group, with the Poisson distribution (log link) and robust error variance. Models will account for provider type and level, and will incorporate clustering by physician team (and separately for nursing unit). Statistical significance will be calculated for the intervention (intervention vs. control) coefficient.

As a secondary outcome for Aim 1, we will assess changes and differences in hand hygiene perception based on response to select questions from PSHW. For Aim 2, mindfulness will be based on responses to FFMQ and well-being will be based on responses to WBI. FFMQ and WBI scales will be scored according to the published algorithms. Descriptive statistics will be used to summarize participant scores from pre- and post-intervention, as well as 6-month post-intervention follow-up assessments. Within-group paired-samples t-tests will be used to test for improvement in participant scores across the baseline, post-intervention (~14 days for physicians and 1-month for nurses), and 6-month post-intervention follow-up periods, for the intervention and control groups separately. Analyses will use list-wise deletion for missing data. Participants not completing all surveys will still be included in any analysis for which they provide data. For all analyses, p values less than 0.05 will be considered significant and all tests will be two-tailed. Analysis of covariance (ANCOVA) models will then be used to assess relative changes in mindfulness, well-being, and hand hygiene perceptions across groups, the most direct test of discriminant validity. In these models, post-test scores will be predicted by group status controlling for pre-test scores.

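### Nurse inference rests on six randomised units, yet the Protocol names no small-sample correction for its robust variance and the SAP omits the clustered model altogether

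*Protocol*

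**What the plan says.** **Randomisation.** Protocol 5.1 (Randomization) allocates separately at each hospital: "At each study site the participating physician teams and nursing units will be randomly assigned into one of two study arms (intervention/control". Table 2 gives the nurse side as "2 units (1 intervention; 1 control) at Ann Arbor VAMC & 4 units (2 intervention; 2 control) at MEDVAMC randomized once & followed for 12-months". Section 5.4 agrees ("1 inpatient hospital unit at Ann Arbor VAMC and 2 units at MEDVAMC will be randomized to receive the intervention", with as many controls), and 5.1 states that units take part once: "This will result in two nursing units from VAAHHS and four nursing units from MEDVAMC participating". That makes three units against three.

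**Protocol analysis.** Section 5.6 models adherence and duration "with the Poisson distribution (log link) and robust error variance". The models account for provider type and level and "will incorporate clustering by physician team (and separately for nursing unit". The intervention coefficient is tested two-sided at 0.05. No bias correction, t reference, permutation test, site term or baseline adherence term is mentioned.

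**Baseline data.** A pre-intervention month is observed on the same units (5.1, Data Collection and Management): "Observations will be conducted for 1 month before the intervention and 1-month after the intervention".

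**SAP.** The December 2025 Data Analysis Plan does not contain the Poisson model. For adherence and duration it lists Fisher's exact test and a t-test. Its mixed models concern mindfulness and well-being, and its random effects cover survey responses within clinician, not nursing units.

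**The concern.** A sandwich variance is estimated from the spread of cluster totals. With six clusters, two of whose degrees of freedom are spent on the arm means, that estimate is too small on average and very unstable. A normal reference allows for neither fault. The thousands of nurse observations per arm sharpen each unit's own rate but leave the number of independent units at six.

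Adherence and duration are the primary Aim 1 outcomes, and nurses are about 130 of the 344 planned participants. If the error rate is not held at 5%, ordinary differences between wards could be reported as an intervention effect, with an interval that is too narrow. If the SAP's tests are what is run on individual observations, the ward structure is ignored entirely.

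**Working it through.** **Plan's own figure.** Neither document gives a false-positive rate or power for nurses. The only related figure is 79.8% power for adherence in the whole sample (Protocol 5.6). With 80% v 88%, 167 per arm, 60 observations each and ICC 0.4, the design effect is 1 + 59 × 0.4 = 24.6, the effective n is 167 × 60 / 24.6 = 407 per arm, and the usual formula gives 87.7%. The stated power is not reproduced, but nothing below depends on it.

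**Step 1. Closed form for a nurse-only model, 3 v 3 equal units, no site gap, no site term.** With n = 3 units per arm the uncorrected sandwich averages (n − 1)/n = 2/3 of the unbiased variance, and the correctly scaled statistic follows t on 4 df. So the type I error is P(|t4| > c × √k), where c is the critical value used and k is the variance relative to unbiased.

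| Variance and reference | c × √k | Type I error |
|---|---|---|
| Uncorrected, z | 1.96 × √(2/3) = 1.600 | 18.5% |
| With factor G/(G−1) = 6/5, z | 1.96 × √0.8 = 1.753 | 15.4% |
| Unbiased, z | 1.960 | 12.2% |
| With factor 6/5, t on 5 df | 2.571 × √0.8 = 2.299 | 8.3% |
| Kauermann-Carroll (unbiased here), t on 4 df | 2.776 | 5.0% |
| Mancl-DeRouen (k = 1.5), t on 4 df | 2.776 × √1.5 = 3.400 | 2.7% |

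Relative to the uncorrected z interval, width is 2.776/1.96 × √1.5 = 1.73 for Kauermann-Carroll and 2.776/1.96 × √2.25 = 2.12 for Mancl-DeRouen.

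**Step 2. Simulation of the Poisson log-link model with six units (beta-binomial data).** The Protocol's ICC is 0.4, for clustering within site, team or unit; all smaller ICCs are assumptions. The site gap of 8-13 points comes from Protocol 2.0: 85% (covert, entry) or 90% (direct) at Ann Arbor against 77% at MEDVAMC.

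| Set-up | Uncorrected, z | G/(G−1), z |
|---|---|---|
| No gap, no site term, ICC 0.01-0.1 | 16-20% | 14-17% |
| No gap, no site term, ICC 0.4 | 10-11% | 7-9% |
| Site term, no gap, ICC 0.01-0.1 | 25-27% | 21-24% |
| Site term, 8-13 point gap, ICC 0.01-0.1 | 23-26% | 19-23% |
| Gap left unmodelled, ICC 0.005-0.4 | 0-15% | 0-12% |
| Pooled, 48 teams + 6 units, ICC 0.02-0.4 | 9-14% | 9-14% |

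An unmodelled gap lowers the rate because it inflates the residual spread between units. The 48 teams are Table 2's two per site per month for 12 months; other parts of the Protocol imply different counts. A bias-corrected variance with t on 4 df gave 4.4-4.7% at ICC 0.01-0.1 and 2.3% at 0.4.

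**Step 3. The SAP's tests, units ignored.** Protocol 5.1 expects 7,040 nurse observations per arm over both months, so one month has about 7,040/2/3 = 1,173 per unit. (The Protocol's own product, 80 × 3 units × 44 days, is 10,560; the conclusion does not turn on which is right.) Type I error is about P(|Z| > 1.96/√(1 + 1,172 × ICC)).

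- ICC 0.001: 1.96/√2.17 = 1.33, giving 18%.
- ICC 0.01: 1.96/√12.7 = 0.55, giving 58% (simulated 59%).
- ICC 0.05: 1.96/√59.6 = 0.25, giving 80%.

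**Step 4. What the allocation alone can show.** Ann Arbor has 2 possible allocations of its two units and MEDVAMC has C(4,2) = 6, so 12 in all. The smallest two-sided p from a within-site randomisation test is 2/12 = 0.167.

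**The case against.** **The rate is conditional.** The Protocol does not say that a normal reference or an uncorrected sandwich will be used; both are inferred from its silence. A reader might quote 17% as the plan's false-positive rate. The documents do not support that: it needs a default estimator, a nurse-only model, unit ICCs that appear nowhere in the documents, and no site difference. This stands, and it is why a range is given.

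**A separate nurse test may not be intended.** Adjusting for provider type suggests one model, and the parenthesis about nursing units may only name a cluster variable. This also stands. It does not remove the problem, since the pooled model still gave 9-14%. But a reader should not infer that six units dominate such a model. On the Protocol's counts (5,760 to 17,100 physician observations per arm over both sites), nurses supply 7,040/24,140 = 29% to 7,040/12,800 = 55% of the data.

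**The 0.167 floor binds a test that nobody plans.** A reader might conclude that no nurse result can properly fall below 0.05. That goes too far: a corrected variance with t on 4 df can do so and holds its level under the model. The floor shows only that such a p-value would rest on model assumptions that six units can barely check.

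**The SAP may govern.** If it does, the robust estimator is not the operative one. The SAP does not say that the clustered model was withdrawn, so that cannot be assumed; if it was, Step 3 shows the position is worse.

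**Conclusion.** The concern holds in conditional form. Six randomised nursing units are certain from four consistent statements in the Protocol, and neither document names a method suited to that number. Under default robust inference in a nurse-only model with no site gap or site term, the type I error is about 15-18% at assumed unit ICCs of 0.01-0.1 and about 7-11% at the Protocol's 0.4. Over the set-ups examined it ranges from about 0 to 27%. The low end arises only when a site gap is left in the error term, so it is not evidence that the method is safe. The SAP's listed tests, applied to individual observations, would be worse at any but a negligible unit ICC.

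The documents do not support a single headline rate, a claim that nurse significance is impossible, or a rule that nurse p-values must be withheld. Analysing change scores instead of adjusting for baseline is a choice, not a necessity: differencing adds variance unless the month-to-month correlation within units exceeds 0.5, which is not known.

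**What to change.** 1. Restore the clustered Poisson model to the SAP as the basis for inference on adherence and duration. Do not use Fisher's exact test or the t-test on individual observations for inference.
2. State whether nurses are analysed in their own model, in a pooled model, or both, and whether site is a term.
3. For nurses, specify a bias-corrected sandwich with t on 4 df, or 6 − 3 = 3 df with a site term. Name one correction in advance: with no site term, Kauermann-Carroll gives about 5% type I error and intervals about 1.7 times as wide; Mancl-DeRouen gives about 2.7% and about 2.1 times as wide.
4. Apply a small-sample correction to any pooled model, and also show the nurse estimate with its corrected interval.
5. Adjust for each unit's pre-intervention adherence, already collected, where degrees of freedom allow.
6. State as a caution that only 12 within-site allocations exist (minimum two-sided randomisation p 0.167), so a nurse p below 0.05 would depend on the model.

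This costs SAP wording and a standard software option, with no new data. The downside is wider nurse intervals, which reflect what six units can show.

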Power - Based on a range of 10%-15% significant percent change in hand hygiene adherence from our pilot data,⁷² we are anticipating an expected increase in hand hygiene adherence due to the intervention from approximately 80% at baseline to 88%-92% at follow-up. We will have 79.8% power to detect this 10% increase based on a fixed total sample size of 334 with a two-sided alpha of 0.05, assuming an average of 60 observed hand hygiene opportunities per provider per measurement time point (i.e., intervention and follow-up), and taking into account clustering of data within site/team/unit (assumed Intraclass Correlation Coefficient=0.4).⁸² For assessing differences in the select PSHW questions we will have 70.1% power to detect an effect size of 0.15.⁸³ For assessing differences in FFMQ and WBI scores, we will have >95% power to detect effect sizes ranging from 0.3 to 0.75 as found in prior studies.^{65,84,85}

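### The stated 79.8% power for adherence does not follow from its own inputs: about 24% or less if ICC 0.4 applies to teams and units (27 per arm), about 88% if it applies within provider

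*Protocol*

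**What the plan says.** Protocol section 5.6 (Power) expects adherence to rise "from approximately 80% at baseline to 88%-92% at follow-up". It then states: "We will have 79.8% power to detect this 10% increase based on a fixed total sample size of 334". The other inputs are a two-sided alpha of 0.05, an average of 60 observed opportunities per provider at each time point, and an allowance described as "taking into account clustering of data within site/team/unit (assumed Intraclass Correlation Coefficient=0.4". No formula, cluster count, cluster size or loss is given.

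The same section plans generalised linear models "with the Poisson distribution (log link) and robust error variance", and says that they "will incorporate clustering by physician team (and separately for nursing unit".

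Section 5.1 makes teams and units the randomised units. Table 2 gives "2 teams each month for 12 months randomized to intervention or control arm at each site", and the Randomization text splits each pair into one intervention and one control team. Table 2 also gives 3 nursing units per arm over the two sites. The SAP has no power section.

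**The concern.** This is the only power figure for adherence, a primary outcome. The paragraph gives enough inputs to recompute it, and the result depends on where the ICC of 0.4 sits.

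At the level the protocol names, the number of teams and units sets a limit that more observations cannot lift. Within provider, the limit comes from the number of providers, and the correlation created by randomising whole teams is ignored. The two readings give very different chances of missing the stated effect, and neither gives the one-in-five chance that 79.8% implies. This affects how a null result on adherence should be read.

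**Working it through.** **Inputs.** From section 5.6: 80% v 88% (0.80 × 1.10 = 0.88), total N 334, 60 observations per provider, ICC 0.4, two-sided alpha 0.05. Assumed: equal arms of 167, made up of 107 physicians and 60 nurses as in the intervention arm of Table 2. That is 107 × 60 = 6,420 physician and 60 × 60 = 3,600 nurse observations per arm, 10,020 in all.

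**Cluster count.** One intervention team per site per month × 12 months × 2 sites = 24 teams per arm, plus 3 units, makes 27. Section 5.1 says that "inpatient care teams are predominately composed of 1 attending, 1 senior resident, 2 interns", so 24 teams supply 24 senior residents and 48 interns. Those are the enrolment figures per arm in section 5.2.

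**Power formula** (pooled two-proportion test, effective n per arm):

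power = Φ{ [ |p2 − p1|√n − 1.96√(2p̄(1 − p̄)) ] / √(p1(1 − p1) + p2(1 − p2)) }

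For 0.80 v 0.88 this is Φ{ (0.08√n − 1.016) / 0.515 }. To obtain 79.8%, n must be 326.8 per arm.

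**Reading A: ICC 0.4 at team/unit level, 27 clusters per arm.**

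- Ceiling as observations per cluster grow without limit: n = 27/0.4 = 67.5, power **24.3%**.
- Actual sizes, efficient weighting: teams of 6,420/24 = 267.5 and units of 3,600/3 = 1,200 observations. n = 24 × 267.5/(1 + 266.5 × 0.4) + 3 × 1,200/(1 + 1,199 × 0.4) = 59.7 + 7.5 = 67.2, power **24.2%**.
- Equal weight per observation: n = 10,020² / (6,420 × 107.6 + 3,600 × 480.6) = 41.5, power **16.6%**.
- Separate models: physicians (24 teams) n = 59.7, power 22.0%; nurses (3 units) n = 7.5, power 6.1%.
- Clusters needed for 79.8%: 326.8 × 0.4 = about 131 per arm.

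A simulation of the planned robust Poisson model (5,000 runs, beta-binomial clusters, terms for arm and provider type) gave 23.9%. Its false-positive rate was 7.1%, so that figure is somewhat flattering.

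**Reading B: ICC 0.4 within provider.** Design effect = 1 + 59 × 0.4 = 24.6; n = 10,020/24.6 = 407.3; power **87.7%**. Unpooled, arcsine, log risk ratio, log odds ratio and continuity-corrected versions give 86.7% to 88.0%. N = 344 gives 88.6%.

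**Inputs that come close to 79.8%.** Each changes or adds something:

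| Change | Power |
|---|---|
| Within-provider ICC 0.4, 20% loss from 334 | 79.7% |
| Within-provider ICC 0.4, coefficient of variation of observations per provider 0.5 | 79.9% |
| Within-provider ICC 0.5 | 80.0% |
| Team/unit ICC 0.4, 80% v 92%, 51 clusters per arm (ceiling) | 79.2% |

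The last row is the 15% increase, not the 10% increase that the sentence refers to.

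**Sensitivity to the team/unit ICC** (80% v 88%, 27 clusters per arm):

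| ICC | Efficient weighting | Equal weighting |
|---|---|---|
| 0.05 | 94% | 79% |
| 0.10 | 71% | 51% |
| 0.20 | 43% | 29% |
| 0.40 | 24% | 17% |

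With 27 clusters, 79.8% corresponds to an ICC of about 0.08 (efficient) or 0.05 (equal).

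**The case against.** **The cluster count is not settled.** Section 5.2 has three teams per arm each month, which makes 36 + 3 = 39 clusters. The Data Collection text in section 5.1 allows up to 48 teams at each site, which makes 48 + 3 = 51. The ceilings are then 39/0.4 = 97.5 (33.0%) and 51/0.4 = 127.5 (41.3%). So the 24% is conditional on 27 clusters, but no count in the text comes near 131. The larger counts are also weakly supported. Thirty-six teams would need 36 seniors and 72 interns per arm, not 24 and 48. The figure of 24 in the observation estimate refers to attending teams, and section 5.1 describes resident blocks of usually 4 weeks "while attendings rotate approximately every 2 weeks". Twelve monthly teams therefore give 24 attending blocks per arm per site. This fits the estimate's lower bound: 8 × 10 × 24 = 1,920.

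**The ICC may be a within-provider value.** An ICC of 0.4 between teams is large, and three levels share one value. On the provider reading, 79.8% is below the computed 87.7%, and 20% loss would explain it almost exactly. This is possible, but the protocol attaches 0.4 to site, team and unit, calls the sample size fixed and states no loss. The origin of the figure cannot be established from the documents. Either way it does not follow from what is written.

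**Baseline data could add power.** The ceiling assumes a comparison without baseline adjustment. A change-from-baseline contrast with an assumed correlation of 0.4 gives 77.5%, but it starts from the provider-level effective sample of 407.3. The adherence model in section 5.6 has no baseline term, and physician teams change monthly.

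**The model itself is uncertain.** Physicians and nurses may be modelled separately, and the SAP lists only Fisher's exact test and the t-test for adherence. Both points stand. Neither helps the figure, since separate models have lower power.

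**Conclusion.** The concern holds. For 80% v 88% with ICC 0.4 at the team/unit level that the protocol names, and 27 clusters per arm, power is at most about 24%, and about 17% with equal weighting of observations. The design would miss the stated effect about three times in four. With the largest count in the text, 51 clusters, the ceiling is about 41%. Reading the increase as 10 percentage points (80% v 90%) with 27 clusters gives 36.7%. With ICC 0.4 within provider, power is about 88%, a miss of about one in eight, and the clustering created by randomisation is not counted.

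The team/unit figures rest on the 24 + 3 cluster count and on a comparison without baseline adjustment; those below the ceiling also assume 167 per arm with 60 observations each. The direction of the error depends on the level of the ICC, which the sponsor must state. The difference between 334 here and the target of 344 in section 5.1 needs reconciling, but does not change the team/unit result.

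**What to change.** Replace 79.8% with power recomputed for the team- and unit-randomised design under the adherence model that will be used, and put it in both the Protocol and the SAP. State:

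- the effect size, and whether the 10% is relative or absolute;
- each ICC and its level: observations within provider, and providers within team or unit;
- teams and units per arm, and observations per cluster;
- the formula or simulation method, the weighting, and any loss or variation in cluster size;
- whether physicians and nurses are analysed together or separately;
- power over a range of team/unit ICCs, for example 0.05 to 0.4.

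If 0.4 stands at team/unit level, say that power for 88% is about one quarter or less with 27 clusters per arm. If 0.4 is a within-provider value, say so and add a team/unit ICC. Reconcile the team counts in sections 5.1 and 5.2, and N (334 v 344).

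The cost is a recalculation and new wording. No participants, data collection or tests change. The stated power may become less favourable.
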